#### 4.1.2.6 Overseas Thorough QTc Study in Healthy Adults ( [REDACTED] )

[REDACTED] (US) is a double-blind (open-label moxifloxacin), randomized study that evaluated the effect of single doses of TAK-385 on QT/QTc intervals in healthy adults.

[REDACTED]

[REDACTED] [5].

## 4.2 Rationale for the Proposed Study

The results of the phase 1 study conducted in England (TAK-385\_C27001) demonstrate the tolerability of multiple doses of TAK-385 (20 to 80 mg) in healthy adult men. Moreover, the plasma concentration of TAK-385 increased as the dose increased, and rose slightly greater than dose proportionality. The blood concentrations of the measured hormones all decreased rapidly with multiple doses of TAK-385 and effective suppression of serum testosterone was sustained throughout the administration period.

[REDACTED]

Because prostate cancer is a sex-hormone dependent disease, and an antitumor effect is expected as a result of lowering hormone concentrations in the blood through administration of TAK-385, it was decided to conduct a phase 1 study in patients with prostate cancer.

This protocol was prepared in accordance with the Good Clinical Practice (GCP).

## **5.0 STUDY OBJECTIVES AND ENDPOINTS**

### **5.1 Objectives**

#### **5.1.1 Primary Objectives**

##### Part A

To evaluate the tolerability and safety of TAK-385 in hormone treatment-naive patients with non-metastatic prostate cancer.

##### Part B

To evaluate the safety of TAK-385 in hormone treatment-naive patients with non-metastatic prostate cancer.

#### **5.1.2 Secondary Objectives**

##### Part A

To evaluate the PK and the effects on serum testosterone of TAK-385 in hormone treatment-naive patients with non-metastatic prostate cancer.

##### Part B

To evaluate the change over time in the prostate-specific antigen (PSA) levels and the PK and effects on serum testosterone of TAK-385 in hormone treatment-naive patients with non-metastatic prostate cancer.

### **5.2 Endpoints**

#### **5.2.1 Primary Endpoints**

##### Part A

Safety: Dose-limiting toxicities (DLTs), AEs, clinical laboratory tests, vital signs, and 12-lead ECGs

##### Part B

Safety: AEs, clinical laboratory tests, vital signs, and 12-lead ECGs

#### **5.2.2 Secondary Endpoints**

##### Part A

PK: Plasma concentrations of unchanged TAK-385

Pharmacodynamics: Serum testosterone concentrations

##### Part B

Efficacy: PSA levels

PK: Plasma concentrations of unchanged TAK-385

Pharmacodynamics: Serum testosterone concentrations

### 5.2.3 Additional Endpoints

#### Part A

Efficacy: PSA levels

Pharmacodynamics: LH, FSH, DHT, and sex hormone binding globulin (SHBG) serum concentrations

#### Part B

Safety: Bone density [6]

Efficacy: Disease progression assessed by PSA, disease progression assessed by imaging

Pharmacodynamics: LH, FSH, DHT, and SHBG serum concentrations

Other: QOL assessments based on the Aging Male's Symptoms (AMS) [7], European Organization for Research and Treatment of Cancer (EORTC)-QLQ-C30 [8, 9, 10], and the Expanded Prostate Cancer Index Composite (EPIC) [11, 12]

## 6.0 STUDY DESIGN AND DESCRIPTION

### 6.1 Study Design

This is a multicenter phase 1, open-label, dose range-finding study to evaluate the tolerability, safety, PK, and pharmacodynamics of TAK-385 alone in hormone treatment-naive Japanese patients with non-metastatic prostate cancer.

This study consists of two parts: Part A, a dose-rising phase, and Part B, an expansion phase. The designs of Part A and Part B are shown in “Study Design and Treatment Schema” (Figure 6.a and Figure 6.b).

In Part A, three to six patients will be enrolled in each cohort. Whether or not the study will proceed to the next cohort or Part B will be determined through assessment of tolerability at the dose in question, based on the incidence of DLT in the evaluation period (treatment initiation to Day 28).

TAK-385 will be taken once a day for 28 days at the doses assigned to each cohort. Cohort 1 will receive a loading dose of 320 mg and a maintenance dose of 80 mg, Cohort 2 will receive a loading dose of 320 mg and a maintenance dose of 120 mg, Cohort 3 will receive a loading dose of 320 mg and a maintenance dose of 160 mg, and Cohort 4 will receive a loading dose of 360 mg and a maintenance dose of 120 mg. The doses will be taken orally at least 30 minutes before breakfast. Patients being switched to a GnRH agonist (eg, leuprorelin) or a GnRH antagonist (eg, degarelix) following the completion of TAK-385 treatment in Part A will first pass through a 1-week observation (no-treatment) period. However, patients whose treatments were discontinued because they met the discontinuation criteria (Section 7.5) during the 28-day treatment period will not have to pass through this observation period.

If tolerability is confirmed in Cohort 2, then the study will proceed to Cohort 3 and Part B simultaneously. The tolerability in Japanese of the maximum dose at which tolerability was found in 28-day multiple dosing in the overseas phase 1 single-/multiple-dose study (TAK-385\_C27001) (160 mg) will be evaluated for the purpose of checking the tolerability of dose escalation to 160 mg in Part B as well as the PK. In the overseas phase 1 single-/multiple-dose study (TAK-385\_C27001), no findings indicative of safety problems were obtained in multiple dosing for 28 days with 160 mg. However, if tolerability is not confirmed in Cohort 2, then a cohort will be added that will receive a loading dose of TAK-385 320 mg and a maintenance dose of 40 mg.

Cohort 4 will be conducted after tolerability is confirmed in Cohort 2. Cohort 4 will be conducted for the purpose of evaluating the tolerability of 360 mg as loading dose in Japanese. 360 mg has been found tolerable in single dosing in the overseas phase 1 single-/multiple-dose study (TAK-385\_C27001) [REDACTED].

[figure not shown]
In Part B, subjects will be randomized to receive study drug (TAK-385 loading dose of 320 mg and maintenance dose of either 80 mg or 120 mg – equal numbers of subjects will be randomized to 80 mg and 120 mg) once a day orally to evaluate safety. In addition to the safety assessments, efficacy assessments will also be performed according

to the study schedule, and study drug will be administered until the discontinuation criteria (Section 7.5) are met for each individual subject. After completing 48 weeks of treatment, subjects may, at the discretion of the investigator, and depending on the wished of the subject, continue receiving study drug (for a maximum of 96 weeks), or they may complete the study and be switched to a GnRH agonist (eg, leuprorelin) or a GnHR antagonist (eg, degarelix), starting from the day after the day of the last dose of TAK-385. Subjects withdrawing from the study will not be replaced.

If no problems with tolerability are found in the additional cohort in Part A, then the study will proceed to Part B with a 40 mg group instead of a 120 mg group (TAK-385 loading dose of 320 mg and maintenance dose of 40 mg).

All subjects who receive study drug, whether in Part A or Part B, will undergo safety follow-up 30 to 40 days after the last dose of TAK-385.

[figure not shown]
Part A (Dose-rising phase)

\*1: If tolerability is not confirmed in Cohort 2, then a cohort will be added which will receive a loading dose of 320 mg and a maintenance dose of 40 mg.

\*2: If a cohort is added, and the additional cohort continues to the end and no problems with tolerability are found, then the study will proceed to Part B.

**Figure 6.a. Study Design and Treatment Schema (Part A)**

\*1: If a cohort is added in Part A, then in Part B 120 mg group will be replaced to 40 mg group, in which subjects will receive loading dose of 320 mg and maintenance dose of 40 mg.

**Figure 6.b Study Design and Treatment Schema (Part B)**

Figure 6.a and Figure 6.b show an overview of the study schedule. See Appendix A through Appendix E for a more detailed schedule of the study tests, observations, and assessments.

**Table 6.a Study Schedule (Part A)**

Screening		Treatment Period		Post-treatment Observation Period	Safety Follow-up
		DLT Evaluation Period (treatment initiation to Day 28)			
Outpatient	Inpatient	Outpatient	Outpatient/Inpatient	Outpatient	
Day -28 to Day -1*1	Day 1*1 to Day 15	Day 16 to Day 28*2	Day 29 to Day 35*2	...	30 to 40 days after the last dose of TAK-385
Screening tests Assessment of eligibility	Admission Treatment initiation Tests/observations	Discharge	Treatment completion Tests/observations	Initiation of other treatment Observations	Tests/observations

\*1: Day -1 and Day 1 are the day before treatment initiation and the day of treatment initiation, respectively.

\*2: Days 27 to 35 are performed either on an outpatient or an inpatient basis.

**Table 6.b Study Schedule (Part B)**

Screening	Treatment Period	Continuation Treatment Period	Safety Follow-up
Outpatient			
Days -28 to -1 *1	Week 1, Day 1 *1 to Week 48, Day 7 *2	Week 49, Day 1 to Week 96, Day 7 *2	30 to 40 days after the last dose of TAK-385
Screening tests Assessment of eligibility, randomization	Tests, observations Treatment initiation Treatment completion	Tests, observations Treatment initiation Treatment completion	Initiation of other treatment Tests, observations

\*1: Day -1 and Day 1 are the day before treatment initiation and the day of treatment initiation, respectively.

\*2: Other treatments may be initiated starting on the day after the day of the last dose of TAK-385 (Week 48, Day 8 or Week 96, Day 8).

### 6.1.1 Cohort/Part Advancement Criteria

Whether or not the study will proceed to the next cohort in Part A will be determined by the study sponsor after consulting the study monitoring committee (SMC) and following a comprehensive evaluation of the safety data based on the number of subjects experiencing DLT in each cohort (Table 6.c). Drug will be administered to the subjects in the next cohort after the decision on cohort advancement is made. See the separately prepared written procedures for detailed study advancement criteria.

In each cohort, if no DLT occurs in even 1 of the 3 subjects during the DLT evaluation period (see Section 6.1.2.2), then the dose will be judged tolerable, and the study will proceed to the next cohort. If a DLT occurs in 1 subject in the DLT evaluation period, and additional 3 subjects will be enrolled in this cohort, and DLT will be evaluated in a total of 6 subjects. If DLT occurs in 1 of these 6 subjects, this dose will be judged tolerable, and the study will proceed to the next cohort. If DLT occurs in 2 or more subjects, the study will be stopped, but if it is determined, after consulting the SMC, that this dose is tolerable, then the study will proceed to the next cohort.

Cohort 3, Cohort 4 and Part B will be conducted after tolerability is confirmed in Cohort 2. Whether or not the study will proceed to Part B will be determined by the study sponsor after consulting the SMC based on a comprehensive evaluation of the tolerability and safety data from Cohort 2 of Part A.

If the study cannot proceed from Cohort 2 to Cohort 3 and Part B because of a tolerability problem, the study will proceed to an additional cohort that will receive a TAK-385 loading dose of 320 mg and a maintenance dose of 40 mg. In this case, as well, 3 subjects will be enrolled, and assessed in the same manner as described above. If the study proceeds to the additional cohort, and continues until the treatment of the additional cohort has been completed, and it is confirmed that no problems with tolerability are found, then the study will proceed to Part B.

If DLT occurs in 2 or more subjects in Cohort 3, then whether or not to increase the dose to 160 mg in Part B will be determined in consultation with the SMC.

Because assessment of the MTD is not the objective of this study, additional subjects will not be enrolled if TAK-385 is found to be tolerable in an evaluation of the 3 subjects in Cohort 3 or Cohort 4, nor will additional subjects be enrolled at lower dose levels if TAK-385 is not found to be tolerable at the dose level initially investigated.

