**Table 6.c Cohort/Part Advancement Criteria**

Number of Subjects With DLT (DLT evaluable subjects)	Cohort	Procedure
0/3	1	Proceed to Cohort 2
	2	Proceed to Cohort 3, Cohort 4 and Part B
	3, 4	Stop
1/3	1 to 4	Add 3 subjects in the same cohort
2/3 or 3/3	1	Stop
	2	Add a cohort *1
	3, 4	Stop
1/6	1	Proceed to Cohort 2
	2	Proceed to Cohort 3, Cohort 4 and Part B
	3, 4	Stop
≥ 2/6	1	Stop
	2	Add a cohort *1
	3, 4	Stop

\*1: TAK-385 loading dose of 320 mg and maintenance dose of 40 mg

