**CONFIDENTIAL**

Part B: If the following conditions are met, the dose may be adjusted, taking efficacy and safety into consideration. Dose adjustment will be performed when the subject is examined by the investigator or sub-investigator.

If the serum testosterone level in an individual patient exceeds 50 ng/dL at Week 5 (Day 29), Week 9 (Day 57), or Week 13 (Day 85), following review of compliance, a one-time upward dose modification (increment of 40 mg daily) will be allowed. After Week 13, the dose will not be increased even if the serum testosterone level exceeds 50 ng/dL.

The dose will not be increased in the 120 mg group before the DLT evaluations have been completed for Cohort 3 in Part A, or if the dose has not been found to be tolerable. Similarly, if tolerability is not found in Cohort 2 in Part A and a 40 mg group is therefore going to be used instead of a 120 mg group, then the dose in the 80 mg group will not be increased.

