## 11.0 STUDY SPECIFIC COMMITTEES

A SMC will be established in this study. The principal duties of the SMC will be to decide when cohorts can progress to the next Part or to make the necessary decisions when it is difficult to judge whether or not DLTs have occurred. This is described in detail in separately prepared procedures.

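### After 2 or more DLTs, Section 6.1.1 allows an exception to stopping that Tables 6.c and 6.d lack, so Cohorts 1 and 2 and the additional cohort have no single decision rule

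*Protocol*

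**What the plan says.** Protocol Section 6.1.1 states a general rule for every Part A cohort; it opens "In each cohort, if no DLT occurs in even 1 of the 3 subjects during the DLT evaluation period". At the upper end it reads "If DLT occurs in 2 or more subjects, the study will be stopped", and the same sentence continues "but if it is determined, after consulting the SMC, that this dose is tolerable, then the study will proceed to the next cohort". Stopping is therefore the default, and proceeding is an exception after consultation with the study monitoring committee (SMC).

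Table 6.c lists the same counts (2/3 or 3/3, and 2 or more of 6) with one action per cohort: Cohort 1 Stop, Cohort 2 Add a cohort, Cohorts 3 and 4 Stop. The only footnote gives the dose of the added cohort. From Cohort 2, "Proceed to Cohort 3, Cohort 4 and Part B" appears only against 0/3 and 1/6.

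A later paragraph of Section 6.1.1 says that if a tolerability problem prevents the move on from Cohort 2, "the study will proceed to an additional cohort that will receive a TAK-385 loading dose of 320 mg and a maintenance dose of 40 mg". That cohort is to be judged by the method already described for the others. Table 6.d gives only Stop for it at 2/3, 3/3 or 2 or more of 6.

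On who decides, Sections 2.0 and 6.1.1 give the decision to the sponsor after consulting the SMC. Section 11.0 says "The principal duties of the SMC will be to decide when cohorts can progress to the next Part".

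**The concern.** Tolerability in Cohort 2 is the gate to Cohorts 3 and 4 and to Part B, and Section 6.2 justifies the Part B doses on tolerability having been confirmed in Cohorts 1 and 2. If text and table give different actions for the same count, that conclusion depends on which passage is followed.

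The consequences are concrete. Take 2 DLTs among the first 3 subjects of Cohort 2. The general sentence stops the study. Its exception moves on with the 120 mg maintenance dose. The table and the later paragraph open a 40 mg cohort and, if that succeeds, replace the 120 mg group of Part B with a 40 mg group (Section 6.1). One set of data has three possible outcomes, with different Part B arms or no Part B at all.

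**Working it through.** **Step 1. The passages side by side, for 2/3, 3/3 or 2 or more of 6 subjects with a DLT**

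| Cohort | Section 6.1.1, general rule | Section 6.1.1, specific paragraph | Table |
|---|---|---|---|
| 1 | Stop, or proceed if judged tolerable | none | 6.c: Stop |
| 2 | Stop, or proceed if judged tolerable | Additional 40 mg cohort | 6.c: Add a cohort |
| Additional | Same method, so Stop, or proceed if judged tolerable | Part B if no tolerability problem | 6.d: Stop |
| 3, 4 | No next cohort to proceed to | Cohort 3: use of 160 mg in Part B goes to the SMC | 6.c: Stop, as also at 0/3 and 1/6 |

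The first three rows conflict. The last does not, because in Table 6.c Stop for Cohorts 3 and 4 appears at the favourable counts too and means only that no cohort follows.

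**Step 2. How often a cohort reaches the disputed counts**

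The plan states no operating characteristic for the Part A rule, so there is no figure to reproduce. Inputs: 3 evaluable subjects, 3 more after 1/3 (Section 6.1.1, Table 6.c, Section 13.3). The true DLT rate p is not in the documents; the values below are assumptions, with subjects taken as independent.

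Probability of proceeding under the table:

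A = (1−p)³ + 3p(1−p)² × (1−p)³

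Probability of reaching the disputed counts:

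Z = 1 − A = [3p²(1−p) + p³] + 3p(1−p)² × [1 − (1−p)³]

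At p = 0.20: (0.8)³ = 0.512 and 3 × 0.2 × 0.64 = 0.384, so A = 0.512 + 0.384 × 0.512 = 0.7086. Directly, Z = (0.096 + 0.008) + 0.384 × 0.488 = 0.104 + 0.1874 = 0.2914.

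| Assumed p | 2/3 or 3/3 | 2 or more of 6 | Z | A |
|---|---|---|---|---|
| 0.05 | 0.0073 | 0.0193 | 0.0266 | 0.9734 |
| 0.10 | 0.0280 | 0.0659 | 0.0939 | 0.9061 |
| 0.20 | 0.1040 | 0.1874 | 0.2914 | 0.7086 |
| 0.33 | 0.2548 | 0.3107 | 0.5656 | 0.4344 |
| 0.50 | 0.5000 | 0.3281 | 0.8281 | 0.1719 |

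**Step 3. What the exception does to the chance of proceeding**

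Let q be the chance that a dose with 2 or more DLTs is nevertheless judged tolerable; q is also an assumption. Under the text the chance of proceeding is A + q(1 − A). At p = 0.20 it is 0.7086 for q = 0, 0.7815 for q = 0.25, 0.8543 for q = 0.5, and 1 for q = 1. The protocol gives nothing from which to fix q.

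**The case against.** The best defence is that text and table were meant to be read together. Section 6.1.1 opens by making advancement a sponsor decision, after consulting the SMC, on an overall review of safety that uses the counts in Table 6.c. On that reading the table lists default actions and the text adds an exception. For Cohort 2 the later paragraph agrees with the table. Committee judgement is a legitimate design choice, and Section 6.1.1 says that finding the MTD is not an objective. It also refers to separate written procedures for detailed advancement criteria.

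Much of this stands. A reader might infer that the protocol allows free escalation after 2 or more DLTs; it does not, since stopping is the default. A reader might also infer that no criterion exists for the exception; the documents show only that none is in the protocol, and the separate procedures may hold one.

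Two wider readings also fail. One is that Cohorts 3 and 4 share the conflict; they have no next cohort. The other is that Section 8.1.3.1 contradicts Section 6.1.1 on Cohort 3. Section 6.1.1 says that after 2 or more DLTs there, "whether or not to increase the dose to 160 mg in Part B will be determined in consultation with the SMC"; Section 8.1.3.1 bars the increase in the 120 mg group before the Cohort 3 DLT evaluation is complete "or if the dose has not been found to be tolerable". These fit in sequence if the consultation settles tolerability and Section 8.1.3.1 then applies the result.

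What the defence does not supply is a statement in the protocol that the table gives defaults only. Nor does it explain why the general sentence says the study stops at a count for which Table 6.c and the later paragraph add a cohort. A subordinate procedure should not have to settle a disagreement inside the protocol.

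**Conclusion.** The point holds for Cohort 1, Cohort 2 and the additional cohort. In the current text, 2 or more DLTs lead to one action under Tables 6.c and 6.d and to a default plus an exception under Section 6.1.1; for Cohort 2 the default differs as well. For the additional cohort, the conflict rests on its being judged by the same method as the others. The protocol does not say which passage prevails.

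The size depends on the unknown DLT rate. The disputed counts are unlikely if DLTs are rare (about 3% per cohort at an assumed rate of 0.05, 9% at 0.10) and common if they are not (29% at 0.20, 57% at 0.33, 83% at 0.50). These are chances of reaching the disputed zone, not of a wrong decision. Until the passages agree, the rule's chance of advancing a dose is defined only as lying between A and 1.

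The sponsor-or-SMC difference is minor: Sections 2.0 and 6.1.1 agree with each other, and only the summary of duties in Section 11.0 departs from them.

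**What to change.** Reconcile Section 6.1.1 with Tables 6.c and 6.d so that each DLT count leads to one stated procedure for each cohort, and make the general sentence agree with the Cohort 2 paragraph. If the SMC exception is intended, enter it in both tables; if not, the text should not carry it. Align Section 11.0 with Section 6.1.1 on who decides. Which action is right is for the sponsor and the SMC.

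In reporting, identify any cohort advanced under the exception as having met the 2-or-more-DLT condition. SAP Section 5.1.3 already tabulates DLTs by treatment group, which in Part A is the assigned cohort, so the events would be visible. What is missing is a statement that the cohort advanced by exception.

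The cost is wording in the protocol and one line of reporting. No subject numbers, assessments or analyses change.

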**Table 6.c Cohort/Part Advancement Criteria**

Number of Subjects With DLT (DLT evaluable subjects)	Cohort	Procedure
0/3	1	Proceed to Cohort 2
	2	Proceed to Cohort 3, Cohort 4 and Part B
	3, 4	Stop
1/3	1 to 4	Add 3 subjects in the same cohort
2/3 or 3/3	1	Stop
	2	Add a cohort *1
	3, 4	Stop
1/6	1	Proceed to Cohort 2
	2	Proceed to Cohort 3, Cohort 4 and Part B
	3, 4	Stop
≥ 2/6	1	Stop
	2	Add a cohort *1
	3, 4	Stop

\*1: TAK-385 loading dose of 320 mg and maintenance dose of 40 mg

**Table 6.d Criteria for Advancing From an Additional Cohort to Part B**

Number of Subjects With DLT (DLT evaluable subjects)	Procedure
0/3	Proceed to Part B
1/3	Add 3 subjects
2/3 or 3/3	Stop
1/6	Proceed to Part B
≥ 2/6	Stop

## 6.1.2 DLT

### 6.1.2.1 Definition of DLT

DLTs are defined as treatment-related AEs that occur within the first 28 days of treatment and that meet one of the criteria described below based on CTCAE Version 4.03 (issued June 14, 2010) [13].

1. Grade 3 or higher toxicity

Clinical laboratory abnormalities meet this criterion if they are found at 2 consecutive time points 7 or more days apart, except for ALT or AST  $> 3 \times$  upper limit of normal (ULN), total bilirubin  $> 2 \times$  ULN, or prothrombin time-international normalized ratio (PT-INR)  $> 1.5$  at 2 time points 2 or more days apart.

2. Either of the following ECG findings at 2 time points 7 or more days apart

- QT/Fridericia corrected QT (QTcF)  $> 500$  msec after treatment initiation
- QT/QTcF interval prolongation  $> 60$  msec postdose

The QTcF interval will be calculated using Fridericia's equation (QT/RR0.33).

If it is difficult to determine whether or not an event is a DLT and the subject who experienced the event should be included in the DLT analysis set, the sponsor will consult the SMC before making a final decision on whether or not the event is a DLT.

Study treatment will be continued until the end of the 28-day treatment period unless a DLT occurs. If a subject is withdrawn from the study for a reason other than a DLT or if treatment compliance is below 80% (23 doses), the subject will be considered ineligible for inclusion in the DLT analysis set, and replacement subjects will be added in order to obtain 3 or 6 evaluable subjects.

